## **3.3      Withdrawal of Subjects From the Study**

### **3.3.1      Reasons for Withdrawal**

Subjects can withdraw consent and discontinue from the study at any time, for any reason, without prejudice to further treatment.

The investigator can also withdraw a subject upon the request of Moderna Therapeutics, Inc. or if Moderna Therapeutics, Inc. terminates the study. Upon occurrence of a serious or intolerable AE, the investigator will confer with the Sponsor or designee. If a subject is discontinued because of an AE, the event will be followed until it is resolved or until stable. In the event of a safety concern that results in withdrawal from further vaccination, the subject will be continued in the trial for safety evaluations.

Every reasonable attempt will be made to follow withdrawn subjects for safety. The reason for subject withdrawal will be documented.

The investigator, in consultation with the Sponsor's medical monitor, **may** withdraw a subject from further vaccination if the subject experiences any of the following:

1. Becomes pregnant;
2. Develops, during the course of the study, symptoms or conditions listed in the exclusion criteria;
3. Experiences an AE (other than reactogenicity) after vaccination that is considered by the investigator to be related to treatment and is of Grade 3 (severe) or higher severity;
4. Experiences an AE or SAE that, in the judgment of the investigator, requires study drug withdrawal due to its nature, severity, or required treatment, regardless of the causal relationship to treatment;
5. Experiences a clinically significant change in clinical laboratory test results, vital signs, or general condition that, in the judgment of the investigator, requires treatment withdrawal;
6. Experiences anaphylaxis clearly attributed to study vaccine; or
7. Experiences generalized urticaria related to the study vaccine.

The reason for withdrawing from further vaccination will be recorded. In addition, if a subject refused further vaccination they will be continued in the trial with all planned visits and assessments. The recording of the reason for vaccination refusal will be documented.

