### **3.4.6        Treatment Compliance**

All doses of study drug will be administered at the study site under direct observation of study site personnel and appropriately recorded (date and time) in the eCRF. Site personnel will confirm that the subject has received the entire dose of study drug. If a subject does not receive study drug or does not receive all of the planned doses, the reason for the missed dose will be recorded in the source documents.

Subjects that miss the second vaccination due to noncompliance with the visit schedule and not due to a cohort pause will still be required to follow the original visit and testing schedule. Specifically, these subjects will be asked to undergo blood collection to comply with a second immune test at 56 (+10) days (Visit 7) following the first vaccination.

The study site is responsible for ensuring subjects comply with the study windows allowed. Should a subject miss a visit, every effort will be made to contact the subject and achieve a visit within the defined visit window. If a subject exceeds their post-vaccination visit in excess of 28 days from the scheduled visit or misses a vaccination schedule by more than 28 days (eg, 28 days beyond the scheduled time of vaccination) then that visit will be classified as a missed

visit and the subject will continue with subsequent visits for Parts A and B of the study. All safety requirements of the missed visit will be captured and included in the follow-up visit (eg, safety laboratory testing, memory aid review for reactogenicity, as applicable).

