For categorical variables, frequencies and percentages will be presented. Continuous variables will be summarized using descriptive statistics (number of subjects, mean, median, standard deviation [SD], minimum, and maximum).

For the summary statistics of all numerical variables unless otherwise specified, minimum and maximum will be displayed to the same level of precision as reported. Mean, median, and confidence intervals (CIs) will be displayed to one level of precision greater than the data collected. Standard deviation will be displayed to two levels of precision greater than the data collected. P-values will be rounded to three decimal places.

When count data are presented, the percentage will be suppressed when the count is zero in order to draw attention to the non-zero counts. A row denoted “Missing” will be included in count tabulations where specified on the shells to account for dropouts and missing values. The denominator for all percentages will be the number of subjects in that treatment within the analysis set of interest, unless otherwise specified.

For the change from Baseline safety summaries, Baseline will be defined as the last non-missing measurement (including repeated and unscheduled assessments) before the first vaccination.

For the immunogenicity analyses, Baseline will be defined as the assessment before the first vaccination.

Study day will be calculated relative to the most recent vaccination. Study day prior to the first vaccination will be calculated as: date of assessment/event – date of first vaccination; study day on or after the date of first vaccination but before the second vaccination (if applicable) will be calculated as: date of assessment/event – date of first vaccination + 1; study day on or after the date of second vaccination will be calculated as: date of assessment/event – date of second vaccination + 1.

Antibody values reported as below the lower limit of quantification (LLOQ) will be replaced by $0.5 \times \text{LLOQ}$. Values that are greater than the upper limit of quantification (ULOQ) will be converted to the ULOQ. Missing results will not be imputed.

All analyses will be conducted using Statistical Analysis System (SAS) Version 9.3 or higher.

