5.1. Sample Size

Approximately 60 subjects (20 per cohort) are planned to be randomized, 15 receiving VAL-181388 and 5 receiving placebo within each cohort. Formal sample size calculations were not performed as this is a descriptive safety and immunogenicity study with no formal null hypotheses being tested.

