5.3.3. Safety Set

The Safety set will include all subjects who received at least 1 dose of study drug (VAL-181388 or placebo). All subjects in the Safety set will be analyzed according to the study drug actually received and not according to the study drug the subject was randomly assigned to receive, in the event there is a discrepancy.

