9.1. Adverse Events

An AE is defined as any untoward medical occurrence associated with the use of a drug in humans, whether or not considered drug related.

A treatment-emergent AE (TEAE) is defined as any event not present before exposure to study drug or any event already present that worsens in intensity or frequency after exposure. Adverse events will also be evaluated by the investigator for the coexistence of medically attended AE which is defined as an AE that leads to an unscheduled visit to a healthcare practitioner.

Adverse events will be coded by preferred term (PT) and system organ class (SOC) using Medical Dictionary for Regulatory Activities (MedDRA) and summarized by treatment group as defined in Section 5, vaccination (first or second), and overall.

All summary tables (except for the overall summary of AEs) will present SOC and PT, will include counts of subjects, and will be based on TEAEs. System organ class will be displayed in descending order of overall frequency and then alphabetically. Preferred term will be displayed in descending order of overall frequency and then alphabetically within SOC. Percentages will be based upon the number of subjects in the Safety set within each treatment group as defined in Section 5.

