- n. Prior medications taken by the subject within the 30 days before providing informed consent will be collected. Concomitant medications include all medications (including vaccinations outside of the trial) taken by the subject from the time of signing the informed consent and through Visit 7.

Table 13-2 **Part B: Schedule of Events**

Procedure	8	9	10	11	12	13	14	15	16	17	18	19 ^a
Study day from 1st dose, if 2nd dose not completed	84	112	140	168	196	224	252	280	308	336	364	392
Study day from 2nd dose, if completed	56	84	112	140	168	196	224	252	280	308	336	364
Window allowance	±7	±7	±7	±7	±15	±7	±7	±7	±7	±7	±7	+15
Type of visit	SC	SC	SC	SC	LV ^b	SC	SC	SC	SC	SC	SC	LV ^b
Safety contact ^c	X	X	X	X		X	X	X	X	X	X	
Blood sample for serum neutralizing antibody titers ^d					X							X
Blood sample for serum antibody titers to CHIKV proteins ^d					X							X
Blood sample for exploratory antibody assays ^d					X							X
Adverse events assessment ^e	X	X	X	X	X	X	X	X	X	X	X	X
Concomitant medications ^f	X	X	X	X	X	X	X	X	X	X	X	X

Abbreviations: CHIKV, chikungunya virus; LV, laboratory visit; SC, safety contact.

- a Visit 19 will be considered the end of study visit.
- b Blood samples for immune persistence will be collected from each subject using a method that maintains the blind (eg, home visits, locally contracted laboratories).
- c Each safety contact will occur by telemedicine (eg, telephone, text message, internet).
- d Excess serum from immunogenicity may be used for future research at the discretion of the Sponsor to better characterize the immune response to the CHIKV protein and/or to assess for cross-reactive antibody responses to other related viruses.
- e Each safety contact will capture outcomes of any adverse event of special interest or serious adverse event that remains unresolved since the last visit or is newly identified through scripted query. Additional data may be requested through medically attended visits, and medications and vaccination will be recorded as part of the medical intake for each telemedicine visit.
- f Receipt of immunomodulators (including vaccines), immunosuppressants, other concomitant medications that could potentially impact immune response will be collected through Visit 19.

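### Second-vaccination adverse event percentages use everyone given at least one dose as denominator, so dose-2 rates are understated whenever a subject misses dose 2

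*SAP*

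**What the plan says.** SAP 9.1 summarizes coded adverse events by treatment group, by vaccination (first or second) and overall. It gives one rule for the percentages: "Percentages will be based upon the number of subjects in the Safety set within each treatment group as defined in Section 5". SAP 5.3.3 defines the set: "The Safety set will include all subjects who received at least 1 dose of study drug". A second dose is not required.

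SAP Section 5 gives the general default: "The denominator for all percentages will be the number of subjects in that treatment within the analysis set of interest, unless otherwise specified". No other section of the SAP sets a denominator for the second vaccination. SAP 9.1.7 also splits solicited reactions by vaccination, and it names neither a denominator nor an analysis set.

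Both documents foresee subjects without a second dose and keep them in follow-up:

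- Protocol 3.3.1, safety withdrawal: "In the event of a safety concern that results in withdrawal from further vaccination, the subject will be continued in the trial for safety evaluations".
- Protocol 3.3.1, refusal: "if a subject refused further vaccination they will be continued in the trial with all planned visits and assessments".
- Protocol 3.4.6 keeps on the original schedule "Subjects that miss the second vaccination due to noncompliance with the visit schedule".
- SAP Table 13-2 has a row headed "Study day from 1st dose, if 2nd dose not completed".

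**The concern.** A subject who never received the second dose adds one to the second-vaccination denominator and can add nothing to its numerator. SAP Section 5 counts study days from the second vaccination only once that vaccination has been given, so no event in such a subject can be placed after dose 2. The printed percentage then mixes exposed and unexposed subjects.

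Solicited and unsolicited events after each vaccination are primary endpoints (SAP 4.2). The error has one direction: dose 2 appears better tolerated than it was.

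It also need not be equal across groups. The grounds for withdrawal from further vaccination in Protocol 3.3.1 include related events of Grade 3 or higher other than reactogenicity. Protocol 1.3 reports that event frequency and severity with the sister vaccines appeared dose related. Missed second doses could therefore gather in the group with the most events and flatten the comparison between doses. That is a plausible mechanism, not a documented one.

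**Working it through.** **Inputs.** SAP 5.1 plans about 60 subjects, 20 per cohort: "15 receiving VAL-181388 and 5 receiving placebo within each cohort". SAP Section 5 pools placebo across cohorts. The number of subjects missing dose 2 (*m*) and the number with an event after dose 2 (*r*) are not in the documents and are assumed below.

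**Planned group sizes.** 3 × 20 = 60 in total. 20 × 3/4 = 15 per vaccine dose. 3 × 5 = 15 for pooled placebo. These agree with the SAP, so each column has a planned N of 15. The SAP has no power calculation to reproduce.

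**Formula.** Let n1 be the subjects given dose 1 (the Safety set) and n2 = n1 − *m* those given dose 2.

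- Percentage under the SAP rule: *r*/n1
- Percentage among dose-2 recipients: *r*/n2
- Ratio of the first to the second: n2/n1, so the relative understatement is *m*/n1

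**Results for n1 = 15.**

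| *m* missing dose 2 | n2 | Factor n2/15 | Relative understatement | *r* = 3: SAP rule vs recipients | *r* = 9: SAP rule vs recipients |
|---|---|---|---|---|---|
| 0 | 15 | 1.000 | 0.0% | 20.0% vs 20.0% | 60.0% vs 60.0% |
| 1 | 14 | 0.933 | 6.7% | 20.0% vs 21.4% | 60.0% vs 64.3% |
| 2 | 13 | 0.867 | 13.3% | 20.0% vs 23.1% | 60.0% vs 69.2% |
| 3 | 12 | 0.800 | 20.0% | 20.0% vs 25.0% | 60.0% vs 75.0% |

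For *m* = 1 to 3 the shortfall is 1.4 to 5.0 points with three subjects with events, and 4.3 to 15.0 points with nine. If *r* = 0, both percentages are zero whatever *m* is.

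**Comparison with placebo.** Protocol 3.6.5.2 plans differences in event proportions between each dose and pooled placebo. Suppose these are taken by vaccination, a vaccine group has 9 subjects with events among 12 dose-2 recipients, and placebo has 3 of 15 with no missed doses. The SAP rule gives 60.0 − 20.0 = 40 points. Among recipients the difference is 75.0 − 20.0 = 55 points.

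**Scale against sampling error.** The exact (Clopper-Pearson) 95% interval for 9/15 is 32.3% to 83.7%. Every shift in the table is well inside that width.

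**Which tables are affected.** Only those split by vaccination, and only the second-vaccination column. All Safety-set subjects received dose 1, so the first-vaccination and overall columns are sound. The overall summary by study part (SAP 9.1.1) and the relatedness, severity and serious-event tables (9.1.2 to 9.1.4) have no vaccination split, and the Safety-set N suits them.

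**The case against.** The strongest case is about importance, not arithmetic.

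- **The effect is conditional.** It is zero if everyone gets dose 2, and the size rests on assumed counts. The protocol also limits missed doses: a vaccination counts as missed only when more than 28 days late (3.4.6), and a study pause suspends the window (3.4.2.2). Replaced or added subjects (3.3.3, 3.4.2.2) could raise N above 15 and soften the factor. All of this stands, and it is why the size is given as a range.
- **The solicited tables are uncertain.** SAP 9.1.7 reaches the Safety-set base only by inference from the Section 5 default, and the table shells, which are not among the documents, may specify otherwise. This stands for 9.1.7. For the events in 9.1 the denominator is explicit, so a shell with another base would contradict the text.
- **A row for missing values may appear.** Section 5 allows one where the shells call for it. It could reveal the unexposed subjects, but it would not change the percentage.
- **The Safety-set percentage is a legitimate pre-specified measure, and the recipients' rate is itself selected,** because subjects stopped after a dose-1 event drop out of it. The selection is real and the fix does not remove it. But a figure that counts people who never had the second dose does not describe how that dose was tolerated.
- **No decision rule uses these percentages.** The pause rules count events, escalation rests on blinded safety review, and no hypothesis is tested. Subject counts (SAP 9.1) and the number given each vaccination (SAP 6.1) let a reader recompute the rate. This limits the consequence. The planned tables would still print the low figure.

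**Conclusion.** The concern holds. As written, SAP 9.1 multiplies each second-vaccination event rate by the fraction of the group that received dose 2. At the planned 15 per group, each missed second dose lowers the printed rate by one fifteenth (6.7%) of its value among recipients. The direction of the error follows from the rule and needs no assumption. Its size depends on how many subjects miss dose 2, which the documents do not give, and it is nil if none do.

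This should be fixed before the tables are produced, although it threatens no formal conclusion: it is a one-directional, avoidable error in a primary safety presentation, small beside the sampling uncertainty and recoverable by a careful reader. The finding is firm for the adverse events under SAP 9.1 and provisional for the solicited reactions under 9.1.7, pending the shells.

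**What to change.** Add to SAP 9.1 and 9.1.7:

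> For summaries by vaccination, the denominator is the number of Safety-set subjects in the treatment group who received that vaccination, and this number is displayed. Overall summaries use the Safety-set N.

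The cost is that sentence and a check that the shells agree. SAP 6.1 already produces the number of subjects receiving each vaccination, so no new data or analysis set is needed. The one drawback is that the first- and second-vaccination columns may then have different denominators, which displaying n makes plain.

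Optionally, show the number of missed second doses and the reasons by group beside the table, so that a reader can judge the selection of who went on to dose 2. The reasons may take more work: SAP 6.1 covers reasons for leaving the study, not for missing a dose, and Protocol 3.4.6 places missed-dose reasons in the source documents without mentioning the case report form. The denominator correction does not depend on this.

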9.1.1. Incidence of Adverse Events

Individual subject listings will be provided for all AEs, AEs leading to withdrawal, AESIs, medically attended AEs.

An overall summary of AEs will be created to include the number and percentage of subjects who experience the following:

- Any unsolicited AE (Part A)
- Any unsolicited treatment-related AE (Part A)
- Any unsolicited AE of grade 3 or 4 (Part A)
- Any unsolicited treatment-related AE of grade 3 or 4 (Part A)
- Any SAE (Part A)

- Any treatment-related SAE (Part A)
- Death (Part A)
- Any AEs leading to withdrawal (Part A)
- Any AE of special interest (Part A)
- Any medically-attended AE (Part A)
- Any SAE (Part B)
- Any treatment-related SAE (Part B)
- Death (Part B)
- Any AEs leading to withdrawal (Part B)
- Any AE of special interest (Part B)

The AEs in Part A will be the AEs that started on or before Visit 7. The AEs in Part B will be the AEs that started after Visit 7.

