#### Vaccine Administration and Dose Escalation Schema

VAL-181388 (or placebo) will be administered as an IM injection (0.5 mL) into the deltoid muscle, preferably in the non-dominant arm, as a 2-dose schedule; the first dose will be given at Visit 1 followed by a second dose 28 days later. VAL-181388 accountability, dose preparation, and administration will be performed by unblinded pharmacy personnel or unblinded designees who will not participate in any other aspect of the study. The remainder of the site staff and all subjects will remain blinded to treatment assignment.

Consent and Screening will occur over a 28-day period prior to randomization. A total of 20 subjects will be randomly assigned to each dose level cohort, 4 subjects (3 VAL-181388 and 1 placebo) to the sentinel safety group and 16 subjects (12 VAL-181388 and 4 placebo) to the expansion group, resulting in 15 subjects being randomly assigned to VAL-181388 and 5 subjects being randomly assigned to placebo (3:1 ratio overall). Subjects meeting all eligibility criteria will receive the first vaccination at Visit 1. Each subject will be monitored in the clinic for at least 1 hour following each vaccination for safety. Assessments will include

vital sign measurements and any immediate reactogenicity. Of note, on the day of vaccination, if a subject is noted to have a systolic or diastolic blood pressure, heart rate, or respiratory rate measurement that shows Grade 2 or higher toxicity after 2 measurements (even after relaxing or resting); has an acute illness; or has an oral temperature  $>38^{\circ}\text{C}$ , the subject should not receive a vaccination on that day and will need to return on subsequent days for their vaccination.

All subjects will return to the clinic at 7 (+3), 17 ( $\pm 3$ ), and 28 (+7) days following each vaccination. In addition, the sentinel safety group will return to the clinic at 1, 2, and 21 (+3) days following the first vaccination. A second vaccination will occur 28 days after the first vaccination (+7 days).

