### **3.4.2.2 Pause Rules**

During the active vaccination period, if any of the following events occur and are assessed to be potentially VAL-181388 related, the study will be paused for further enrollment and vaccination and an unscheduled SMC will be convened to assess specific data concerns and make recommendations:

- Two or more severe reactogenicity events of the same nature (whether systemic or local) within a dose cohort following any single (eg, the first, the second) vaccination
- Two or more Grade 3 (or greater) laboratory toxicities within a cohort and of the same nature
- One or more SAEs assessed as vaccine related, including any systemic hypersensitivity reaction

An unscheduled SMC may also be convened (with vaccination pausing if deemed necessary), by the investigator, IST, or Sponsor, if any other significant safety or tolerability issues are identified in the comprehensive review of available data that warrant further evaluation before additional subjects are dosed. This may include emerging nonclinical data, clinically relevant AEs, or relevant data from other sources indicating safety concerns even if the event(s) per se does not meet the criteria specified in this section.

Should a pause be triggered in the study, then each subject's visits will continue until the next scheduled vaccination visit. Should a pause affect a subject's vaccination visit, then the window for that subject's vaccination visit will be suspended until the pause is lifted and vaccination can resume. Once the pause is lifted at the site, vaccination should be reinstated as soon as possible. Visits should thereafter be scheduled as if they had received their second vaccination within the 28 (+7) day time window.

Should a pause be prolonged such that the vaccination sequence cannot establish a 28 (+ 7) day time window, the Sponsor has the option to add additional subjects in a dosing cohort to achieve the original number of subjects planned to be dosed within the 28 (+7) day time window. If a subject is in the screening period during this pause and more than 28 days has transpired, they may be rescreened for study eligibility as long as they continue to provide consent to participate in the study.

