### **3.5.2 Completion of Memory Aid**

The memory aid utilized will be a diary card (paper or electronic device) and is a method to record systematic collection of AE information from the subject; this information is subject to potential change based on further questioning and/or follow-up by study staff. Each subject will be instructed to complete a memory aid to describe:

- Solicited local and systemic AEs (Section [3.5.6](#)) occurring (with appropriate documentation to allow severity grading by the investigator) during the day of each dose administration and for the following 7 days
  - Daily oral body temperature measurement is to be performed at approximately the same time each day using the thermometer provided by the study site. If body temperature is taken more than once in a given day, only the highest temperature reading will be recorded.
  - For solicited local AEs that require measurement, the measurement of size will be performed using the ruler provided by the study site.
- All medications (excluding vitamins and minerals) taken during the day of each vaccine administration and for the following 28 days
- Any unsolicited AE during the first 28 days following each vaccination

Study staff will review the information regarding solicited and unsolicited AEs, temperatures, and concomitant medications during the clinic visit. This information will be recorded in the subject's source documents and the eCRF.

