### **3.5.7.2 Eliciting and Documenting Adverse Events**

The investigator is responsible for ensuring that all AEs and SAEs are recorded in the eCRF and reported to Moderna Therapeutics, Inc. In Part A of the study, AEs will be assessed from the time of the first dose administration at Visit 1 through Visit 7. However, for the time period after the ICF is signed until before receiving the study drug, AEs will only be recorded when they are defined as one or more of the following: SAEs, AESIs, or AEs leading to study withdrawal. In Part B of the study, AESIs and SAEs will be assessed from Visit 8 through Visit 19. Any AEs occurring before receipt of the study drug will be analyzed separately from TEAEs.

At every clinic visit or telephone contact, subjects will be asked a standard question to elicit any medically related changes in their well-being according to the scripts provided. Subjects will also be asked if they have been hospitalized, had any accidents, used any new medications, or changed concomitant medication regimens (both prescription and over-the-counter medications).

In addition to subject observations, data from clinical laboratory test results, physical examination findings, or other documents relevant to subject safety classified as an AE will be documented on the AE page of the eCRF.

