4.2. Study Endpoints

The following are the safety (primary) endpoints:

Part A:

- Solicited AEs (local and systemic reactogenicity events) collected for 7 days following each vaccination with toxicity grading
- Unsolicited AEs collected for 28 days following each vaccination; additional classification if serious, medically attended, or an AESI
- Safety laboratory test results (serum chemistry, hematology, coagulation, and urinalysis) with toxicity grading
- Vital sign measurements with toxicity grading and physical examination findings

Part B:

- Serious AEs and AESIs through 1 year (or until resolved, whichever occurs first) following the last vaccination

The immunogenicity assessments are as follows:

Part A:

- Serum neutralizing antibody titers to CHIKV proteins (baseline and 28 days after each vaccination)
- Serum binding antibody titers (immunoglobulin G [IgG]) to CHIKV proteins (baseline and 28 days after each vaccination)
- Exploratory antibody assays may be performed with excess serum to assess for cross-reactivity to related viruses at the discretion of the Sponsor

- Additional exploratory assays based upon current research may be performed with excess serum to better characterize the immune response to the CHIKV proteins at the discretion of the Sponsor

Part B:

- Serum neutralizing antibody titers to CHIKV (at 6 and 12 months after the last vaccination)
- Serum binding antibody titers (IgG) to CHIKV-specific proteins (at 6 and 12 months after the last vaccination)
- Exploratory antibody assays may be performed with excess serum to assess for cross-reactivity to related viruses at the discretion of the Sponsor
- Additional exploratory assays based upon current research may be performed with excess serum to better characterize the immune response to the CHIKV proteins at the discretion of the Sponsor

5. General Statistical Considerations

All data collected will be presented in listings. Subjects will be identified in the listings by the subject identification number concatenated with the site number.

Data from subjects excluded from an analysis set will be presented in the data listings but not included in the calculation of summary statistics for the corresponding analysis set.

Data from subjects receiving placebo will be pooled across cohorts for all presentations.

Unless otherwise specified, the following treatment groups will be used for summary purposes:

- 25 µg VAL-181388
- 50 µg VAL-181388
- 100 µg VAL-181388
- Placebo

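### SAP 9.1.1 counts Part A unsolicited AEs up to Visit 7, while the primary endpoint is 28 days after each vaccination, so the tabulated period follows visit timing

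*SAP*

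**What the plan says.** The endpoint sections agree with each other. SAP 4.2 lists as a primary safety endpoint "Unsolicited AEs collected for 28 days following each vaccination; additional classification if serious, medically attended, or an AESI", and protocol 3.6.1 has the same wording. The memory aid in protocol 3.5.2 covers the same period: "Any unsolicited AE during the first 28 days following each vaccination".

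The tabulation rule is different. SAP 9.1.1 states "The AEs in Part A will be the AEs that started on or before Visit 7", and events that start later belong to Part B. Sections 9.1 to 9.1.7 of the SAP put no 28-day limit on unsolicited AEs. SAP 8.1 does apply such a limit, but to concomitant medications.

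The Visit 7 boundary comes from the collection rule in protocol 3.5.7.2: "In Part A of the study, AEs will be assessed from the time of the first dose administration at Visit 1 through Visit 7". The same section adds that "Any AEs occurring before receipt of the study drug will be analyzed separately from TEAEs".

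Visit 7 is not a fixed day. Protocol 3.1 sets the second injection at 28 (+7) days after the first and brings subjects back at 7, 17 "and 28 (+7) days following each vaccination". Protocol 3.4.6 puts Visit 7 at 56 (+10) days after dose 1 for a subject who misses dose 2 through noncompliance with the visit schedule. Under protocol 3.4.2.2, if a pause affects a vaccination visit, "the window for that subject's vaccination visit will be suspended until the pause is lifted and vaccination can resume". No maximum is given, and later visits follow the delayed dose.

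**The concern.** A programmer who follows SAP 9.1.1 will not produce the stated endpoint. The rows for any unsolicited AE, related AEs and grade 3 or 4 AEs will include events with onset outside both 28-day windows, and how many depends on when each subject attended. The by-vaccination tables in SAP 9.1 are affected too: a subject without dose 2 carries 56 to 66 days under the first vaccination, against 28 to 35 days for a two-dose subject inside the window.

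The comparison at stake is the difference in AE proportions between each dose level and pooled placebo, planned in protocol 3.6.5.2. The next cohort opens only after 7-day data following dose 2 have been reviewed, so a pause during the dosing interval delays dose 2 in one cohort. That cohort holds all 15 vaccine recipients at its dose but only 5 of the 15 pooled placebo subjects. Part A would then be longer, on average, for that dose than for its comparator.

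**Working it through.** **Inputs.** Dose 2 at day 28 to 35 after dose 1, and Visit 7 at 28 to 35 days after dose 2 (protocol 3.1). Visit 7 at day 56 to 66 if dose 2 is missed (protocol 3.4.6). 15 vaccine and 5 placebo subjects per cohort (SAP 5.1), with placebo pooled to 15 (SAP 5). The documents give no pause length and no background AE rate, so both are assumptions below.

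**1. The plan's own figure.** Nominal Visit 7 is 28 + 28 = 56 days after dose 1. This matches protocol 3.4.6 and equals two 28-day windows end to end.

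**2. Range without a pause.**
- Two doses, all visits in window: 28 + 28 = 56 to 35 + 35 = 70 days. The excess over 56 is at most 14 days (14/56 = 25%).
- Dose 2 missed: 56 to 66 days against an endpoint window of 28 days, a ratio of 56/28 = 2.0 to 66/28 = 2.4.

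**3. A pause of D days that delays a whole cohort in full.** The paused dose has 56 + D days. Pooled placebo has a mean of [10 × 56 + 5 × (56 + D)]/15 = 56 + D/3 days. For D = 28 this is 84 against 65.3 days, a gap of 18.7 days.

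**4. Effect on the proportion with any unsolicited AE.** Assume no vaccine effect and a constant background rate r, so P(t) = 1 − exp(−r·t). Pooled placebo is [5 × P(paused) + 10 × P(56)]/15, so the spurious difference is (2/3) × [P(paused) − P(56)].

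Two cases with D = 28:
- *Full delay:* P(paused) = P(84).
- *Spread delay:* due dates fall evenly over the pause, so delays run evenly from 0 to 28 days and P(paused) = 1 − exp(−56r) × [1 − exp(−28r)]/(28r).

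| r per 100 person-days | P(56) | Full delay: dose vs placebo | Difference (points) | Spread delay: dose vs placebo | Difference (points) |
|---|---|---|---|---|---|
| 0.5 | 0.244 | 0.343 vs 0.277 | +6.6 | 0.295 vs 0.261 | +3.4 |
| 1 | 0.429 | 0.568 vs 0.475 | +9.3 | 0.502 vs 0.453 | +4.9 |
| 2 | 0.674 | 0.814 vs 0.720 | +9.3 | 0.750 vs 0.699 | +5.1 |

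A fully delaying 14-day pause gives +3.4 to +5.3 points at the same rates.

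**5. Scale.** The standard error of a difference between two groups of 15 is √[p₁(1 − p₁)/15 + p₂(1 − p₂)/15]. In the full-delay column this is 15.3 to 18.2 points.

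**6. After the fix.** With 28 days after each injection, a two-dose subject contributes 56 days whatever the visit dates or pause, and the gap in step 3 becomes zero. A single-dose subject contributes 28 days.

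**The case against.** The strongest reply is that the SAP follows the protocol. Part A ends at Visit 7, AEs are assessed through Visit 7, and the memory-aid row for unsolicited AEs in Table 6-1 runs to Visit 7. On nominal timing the two definitions coincide at 56 days. This stands as an explanation: the mismatch already exists inside the protocol, between its endpoint and its collection period. It does not settle what the endpoint table should count, because collecting through Visit 7 does not prevent tabulating to 28 days.

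The pause scenario is also conditional. No document predicts a pause. Full delay requires essentially every subject to fall due for dose 2 at its start, yet sentinels are dosed at least 7 days before the other 16 subjects are randomized, and anyone already given dose 2 is unaffected. The spread case is the milder figure, and a pause that catches only part of a cohort gives less again. Even the largest difference is about half a standard error in a descriptive study without hypothesis tests. All of this stands and limits the size.

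Part of the remedy exists already. SAP 9.1 summarizes by vaccination, SAP 5 counts study day from the most recent vaccination, and all AEs are listed. None of these limits onset to 28 days.

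Finally, a pure 28-day rule has its own cost. Single-dose subjects would contribute 28 days against 56 in one denominator, and dose 2 may be withheld after a related Grade 3 AE (protocol 3.3.1), so the shortening could depend on treatment. Late medically attended or grade 3 to 4 AEs would also leave the tables. This stands, and is why the Visit 7 summary should be kept alongside.

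**Conclusion.** The point holds as a mismatch between the stated primary endpoint and the rule that produces its tables. It follows from the documents alone: 56 to 70 days for in-window two-dose subjects, 56 to 66 days instead of 28 after a missed dose 2, and an open-ended period after a pause.

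Bias between doses is a contingent consequence. It needs a pause that delays dose 2 in one cohort. For an assumed 28-day pause, a constant background rate of 0.5 to 2 per 100 person-days and no vaccine effect, it is about 3 to 5 points with due dates spread over the pause, and at most about 7 to 9 with full delay of the cohort.

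A reader might infer two stronger things that the documents do not support:

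- **That the plan as written is biased against a dose.** Without a pause or missed doses, the drift is at most 14 days and the design ties it to no dose group.
- **That SAEs and AESIs recorded between consent and dose 1 will enter the Part A rows.** SAP 9.1 excepts the overall summary in the sentence that bases tables on TEAEs, but that exception can equally mean only that this table shows no SOC and PT. Protocol 3.5.7.2 separates pre-dose events. One clarifying sentence is warranted; a finding of error is not.

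**What to change.** In SAP 9.1.1 and the tables it governs:

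- Count the unsolicited-AE rows (any, related, grade 3 or 4) and the by-vaccination SOC and PT tables as AEs with onset after the injection and within 28 days after each vaccination. Assign each AE to the most recent vaccination.
- Base by-vaccination percentages on subjects who received that vaccination.
- Keep the present through-Visit-7 summary as a supplementary table, so that late AEs stay tabulated.
- Keep Visit 7 as the Part A/Part B split for SAEs, AESIs, deaths, medically attended AEs and withdrawals.
- State that all rows of the overall summary are limited to treatment-emergent events, in line with protocol 3.5.7.2.

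The cost is SAP wording, one derivation flag and one extra table. Data collection, visit windows and pause rules are untouched. The remaining drawback is the shorter period that single-dose subjects contribute to the overall 28-day row; the by-vaccination denominators and the supplementary table make it visible.
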